1.0 Protocol Summary

| Study Dumoso | • Patient Cohort |
|--|---|
| Study Purpose | Patient Conort The purpose of the research is to implement and evaluate a nurse-led clinical program designed to improve screening, referral, and treatment for sexual dysfunction in gynecological cancer patients. Nurse Cohort The purpose of the research is to increase knowledge and confidence in sexual dysfunction screening, referral and treatment among gynecologic cancer nurses. |
| Research Procedures | The primary research procedures are: |
| | Patient Cohort Assess effectiveness of the nurse led clinical sexual dysfunction program via number of referrals and treatments in the chart before and after the intervention in gynecologic cancer patients. Assess improvement in sexual dysfunction in gynecologic cancer survivors via the Female Sexual Function Index (FSFI). Nurse Cohort Increase gynecologic nurses' knowledge and confidence of sexual dysfunction screening, referral and treatment using the Knowledge, Attitude, and Practice Survey in Healthcare (KAP), and the Evidence Based Nursing Practice Self-Efficacy Scale (EPSE). |
| Subject Population | Patient Cohort The study will enroll gynecological cancer patients who have completed treatment within the past twelve months. Nurse Cohort The study will enroll gynecologic oncology nurses in an outpatient comprehensive cancer center |
| Duration of Subject's Participation | Patient Cohort The study involves participation of patient subjects at multiple time points. The total patient study participation is 12 weeks. Nurse Cohort The study includes the participation of nurse subjects at two time points: pre and post education of sexual dysfunction screening and treatment. |

| • The total study duration is 2 hours. Nurses will have 4 |
|---|
| weeks to complete the 2 hours. |

2.0 Background, Rationale

- Sexual dysfunction (SD) is a common issue among female cancer survivors, profoundly affecting their quality of life (Sousa Rodrigues-Guedes et al., 2022). Sexual dysfunction is highly prevalent among gynecological oncology patients, with rates reaching up to 90% (Kaufman et al., 2024).
- Discussion about sexual dysfunction between patients and healthcare providers are often limited, with reports indicating that such conversations occur in as few as 27.9% of cases (Sousa Rodrigues-Guedes et al., 2022). Several barriers contribute to this communication gap, including healthcare providers feeling unqualified or unprepared, facing time constraints, lacking referral resources, possessing limited knowledge, and being unsure how to broach the topic (Chou et al., 2023; Kaufman et al., 2024; Trachtenberg et al., 2019).
- Unaddressed sexual dysfunction can contribute to psychological distress, which in turn
 is associated with higher cancer incidence, increased cancer-specific mortality, and
 worsened survival outcomes (Wang et al., 2020).
- Sexual dysfunction negatively impacts mental, emotional, and relational well-being, contributing to lower HRQOL, an important predictor of morbidity and all-cause mortality in cancer survivors (DuMontier et al., 2018; Sitlinger & Zafar, 2019).
- Depression and anxiety linked to untreated sexual dysfunction can lead to higher emergency department use, longer hospital stays, and healthcare costs that are nearly double those of patients without these conditions (Birch et al., 2023; Masbach et al., 2020).
- Many interventions for sexual health have been investigated. These include
 psychoeducational and psychotherapeutic interventions, exercise programs, hormone
 replacement therapy administration, pelvic floor physical therapy, and health provider
 and patient education (Sopfe et al., 2021).
- There has been success in nurse-led rehabilitation programs that focus on a multimodal approach to sexual dysfunction in gynecological cancer survivors (Chow et al., 2023; Seaborne et al., 2021; Hungr et al., 2020).

3.0 Study Purpose and Objectives

Patient Cohort

The primary objectives of this study are to implement and evaluate the effectiveness of a nurse led clinical program to improve sexual dysfunction among gynecological cancer survivors. The patient's outcomes will be measured via the Female Sexual Function Index (FSFI).

The secondary objectives of this study are to improve gynecologic cancer nurses' knowledge and confidence in the topic of sexual dysfunction screening, treatment, and referral using the Knowledge, Attitude, and Practice Survey in Healthcare (KAP), and the Evidence Based Nursing Practice Self-Efficacy Scale (EPSE).

4.0 Study Population

4.1 Inclusion Criteria

Patient Cohort

- Patients with a gynecologic cancer history
- Patients ages 30-65 years old
- Patients must have completed cancer treatment within the past 12 months
- Patients may be on maintenance therapy

Nurse Cohort

- Registered Nurses 18 years or older
- Registered Nurses working in the gynecologic clinic in the outpatient cancer center

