4.3.1 Consent Description

Patient Cohort

APP/Co-PI, [name], will identify patients via medical records. Potential participants will be contacted directly by APP/Co-PI through an IRB-approved email message based on the HRP-661 Direct to Patient Recruitment Letter. The patient will be given the opportunity to decline to be contacted, as indicated in the email. The APP/Co-PI will give the patient a reasonable amount of time to agree to or decline to be contacted after the email is sent. If the patient has already been approached by a treating physician about participation in this study, or if the patient has been sent the recruitment letter and has not declined to be contacted, the APP/Co-PI will reach out to the by phone. In the first conversation with the potential participant, the APP/Co-PI will explain the study carefully by going through the consent form via telephone script. The patient will be given the option to decline or defer participation, or, if interested, to sign the ICF by electronic signature via Docusign. The APP/Co-PI will send the potential participant the DocuSign link to the electronic consent form. Those who prefer to complete the consent form in person will have the option to do so electronically on a tablet or on paper. Patients will be highly encouraged to follow up with the study team before signing should they have any additional questions. If the patient indicates they plan to sign the consent form, the APP/Co-PI will follow up with another phone call if necessary to answer any remaining questions. All patients who participate will receive a surveillance visit with an additional focus on sexual health component with the Advanced Practice Provider ([name]). However, only patients who complete the pre-and post-FSFI survey and complete the APP visit will be involved in the study. The FSFI survey will be submitted to the patient and completed via REDcap.

Nurse Cohort

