5.2 Study Design and Duration

Patient Cohort

The study design is an evidence-based practice (EBP) study and includes the implementation and evaluation of a nurse led sexual health clinical program via the FSFI survey. The duration of study participation is 12 weeks. The goal for patients is to have 80% of participating patients to complete pre and post surveys and APP visit as part of their sexual health clinical program, with 30% of patients reporting improvement in sexual dysfunction via the FSFI score.

Nurse Cohort

The study design is an EBP study and includes two surveys in the Registered Nurse participants that includes KAP and EPBSE. The duration of study participation is 4 weeks. The goal is to have 100% of the gynecology oncology registered nurses to participate in the survey and sexual dysfunction education.

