6.3 Data Elements

- The following data points will be collected:
- The following data points will be collected from patients:
 - o Age
 - o Gender
 - Race
 - Marital Status
 - Gender Identity
 - Sexual orientation
 - o MRN
 - Preferred language
 - Medical history
 - Hospital Diagnosis
 - o Date of surgery
 - o Date of chemotherapy
 - Date of radiation
- If applicable the following data points will also be collected from patients
 - o Prior reports of sexual dysfunction
 - o Referrals and visits with Pelvic floor physical therapists, Physical Rehabilitation, Genitourinary team, Social Work, and Psychology teams.
- The following data points will be collected from nurses:
 - o Age
 - Gender
 - Current work unit
 - Current position
 - Length of time in their current position

The information to be accessed and reviewed is that which is minimally necessary to achieve the goals of this research.

| TTT | | | T 1 | | • 🕰 | |
|-----|---|-----------|-----|-----|-------|---|
| ш | v | Λ | | ant | ifier | • |
| | | \neg | | | | |

| ☐ No HIPAA Identifiers will be collected for this study (or select the |
|---|
| identifiers from the following list). The investigators will not attempt |
| to re-identify subjects from the collected data. |
| ⊠ Medical Record Number |
| □ Name |
| ☐ Address (all geographic sub-divisions smaller than state, including street |
| address, city county, and zip code) |
| ⋈ All elements (except years) of dates (including birthdate, admission date, |
| discharge date, date of death, and exact age if over 89) |
| ☐ Telephone Numbers |
| ☐ Fax Numbers |
| ⊠ Email Address |
| □ Social Security Number |
| ☐ Health plan beneficiary number |
| ☐ Account Number |
| ☐ Certificate or license number |
| ☐ Vehicle identifiers and serial numbers, including license plate numbers |
| ☐ Device identifiers and serial numbers |
| □ Web URL |
| ☐ Internet Protocol (IP) Address |
| ☐ Finger or Voice Print |
| ☐ Photographic Image (photographic images are not limited to the face) |
| ☐ Any other characteristic that could uniquely identify the individual |

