8.3 Statistical Analysis Methodologies

Patient Cohort

- This pilot study will obtain estimates of the following parameters:
- The patient subjects will be, at most, 35 subjects due to the available population and limited timeframe.

- In this survey/questionnaire study, we will assess patients' sexual function in aggregate form.
- The FSFI addresses five domains to include desire and subjective arousal, lubrication, orgasm, satisfaction, and pain/discomfort. It encompasses nineteen self-measurement items that provides a score on overall levels of sexual function (Meston et al., 2020). A Likert scale is used from 1 to 5, with higher scores indicating greater levels of sexual function on the specific item. FSFI is scored in two ways; individual domains and total FSFI score by taking a sum of all scores (Meston et al., 2020).
- We hypothesize that 30% of participants have an improvement in FSFI scores indicated by a ½ standard deviation.
- The project will utilize both QI Macros and Intellectus Statistics to measure the changes in patient sexual function. The analysis will incorporate statistical methods such as run charts, control charts, and t-tests to assess sexual function in patients before and after the intervention. More specifically regarding t-tests with the FSFI tool, we will compare pre and post intervention using paired t-tests.

- The nurse subjects will be at most five.
- In this survey/questionnaire study, we will assess nurses' responses in aggregate form. The KAP survey is comprised of 24 items, each assessed using a 4-point likert scale (Xie et al., 2023).
- Participants evaluate their knowledge and skills on a scale ranging from 1 (inadequate) to 4 (more than adequate). Similarly, they rate the frequency of their practice for each item, from 1 (never) to 4 (almost always). Scores for each subscale, knowledge, attitudes, and practices, range from 24 to 96 (Xie et al., 2023). The total score for the KAP survey is obtained by summing the scores across all subscales, with higher scores indicating greater levels of knowledge, more positive attitudes, and more consistent practices (Xie et al., 2023).
- We hypothesize that 50% of nurses have an increase in KAP scores indicated by a ½ standard deviation.

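### The FSFI objective claims program effectiveness, but a single-cohort before-after comparison cannot separate a program effect from any other change

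*Protocol*

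**What the plan says.** - **Objective.** Protocol Section 3.0 makes it a primary objective to "implement and evaluate the effectiveness of a nurse led clinical program to improve sexual dysfunction among gynecological cancer survivors" and names FSFI as the patient outcome. The Protocol Summary (Section 1.0) is worded differently. There, effectiveness is assessed by counts of referrals and treatments, and the FSFI aim is only to assess improvement.
- **Design.** Section 5.2 says the study "includes the implementation and evaluation of a nurse led sexual health clinical program via the FSFI survey". It describes no comparison group, wait-list or historical rate for FSFI. Section 4.3.1 exposes everyone: "All patients who participate will receive a surveillance visit with an additional focus on sexual health component".
- **Population.** Section 4.1 requires: "Patients must have completed cancer treatment within the past 12 months". It adds: "Patients may be on maintenance therapy". It sets no minimum time since treatment.
- **Measurement.** Sections 5.1 and 5.3 give two FSFI assessments, one before the visit and one at the end of the study, 8-10 weeks after it.
- **Analysis.** Section 8.3 states: "we will compare pre and post intervention using paired t-tests". It also hypothesizes that 30% of participants improve by ½ SD. Sections 5.2 and 8.1 repeat 30% improving as a goal.
- **Scope.** Section 8.2 calls the study a pilot and an evidence-based practice project, meant to inform a change of practice rather than to produce generalizable findings. The Protocol states no limitation of the before-after comparison.

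**The concern.** Effectiveness is a causal claim. It needs some account of what FSFI would have done over the same weeks without the program, and this design supplies none. The entry window makes that concrete. A patient just out of treatment, one nearly a year out and one on maintenance therapy may each be changing for reasons unrelated to the visit, and all are pooled. The mean change then depends partly on who happens to enroll.

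What is at stake is the conclusion. Under Section 3.0 as worded, a favorable paired t-test or a responder share of 30% could be written up as showing that the program works. A clinic could change practice on a difference that the program may not have produced. The reverse can also happen: if patients would otherwise have worsened, a useful program could look inert.

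**Working it through.** **Inputs from the Protocol.** Section 8.1: 35 patients, 80% completing, so 35 × 0.80 = 28. Goal: 30% improving by ½ SD; 0.30 × 28 = 8.4, so at least 9 of 28. The Protocol states no alpha, power, SD, correlation or natural rate of change, so it offers no figure to reproduce.

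**Assumptions.** The ½ SD is taken as half a baseline SD. Scores are normal with equal SD at both times. The pre-post correlation r is 0.6-0.8, with 0.9 as a sensitivity value. Drift d, the mean change without any program, is 0 to 0.3 baseline SD. The test is two-sided at 5%. The program effect is zero.

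**Step 1: what the paired difference estimates.** Mean change = drift + program effect. One cohort with one score on each side of the visit gives one number for two unknowns. This needs none of the numerical assumptions. Run and control charts do not help, because each patient has only two FSFI points.

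**Step 2: share gaining at least ½ SD.** The SD of change is √(2(1−r)), which is 0.894, 0.775 and 0.632 at r = 0.6, 0.7 and 0.8. The share is 1 − Φ((0.5 − d)/√(2(1−r))). For example, at r = 0.7:
- d = 0: 1 − Φ(0.5/0.775) = 26%
- d = 0.2: 1 − Φ(0.3/0.775) = 35%

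**Step 3: chance of an apparent success with 28 completers.** The goal is a binomial tail at 9 or more. The t-test column is the chance of a significant improvement, from the noncentral t with noncentrality d√28/√(2(1−r)).

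| Drift d | r | Share gaining ≥ ½ SD | Chance goal is met | Chance t-test shows improvement |
|---|---|---|---|---|
| 0 | 0.6 / 0.7 / 0.8 | 29% / 26% / 21% | 0.42 / 0.29 / 0.13 | 0.025 each |
| 0.2 | 0.6 / 0.7 / 0.8 | 37% / 35% / 32% | 0.76 / 0.69 / 0.55 | 0.21 / 0.26 / 0.37 |
| 0.3 | 0.6 / 0.7 / 0.8 | 41% / 40% / 38% | 0.88 / 0.85 / 0.78 | 0.40 / 0.51 / 0.68 |

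At r = 0.9 the shares are 13%, 25% and 33% for d = 0, 0.2 and 0.3, so the 30% mark is not always crossed.

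**Step 4: how much is drift and how much is noise.** At r = 0.6-0.8, a drift of 0.2 SD adds about 8-10 percentage points (37 − 29 = 8 at r = 0.6; unrounded, 31.8 − 21.5 = 10.3 at r = 0.8). Most of the 32-37% is ordinary variation around a ½ SD threshold.

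**Step 5: the opposite direction.** If patients would have declined by 0.2 SD and the program added 0.2 SD, the net change is −0.2 + 0.2 = 0. The first row then applies, and a real effect is invisible.

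**Step 6: can time since treatment rescue the comparison?** Suppose the 28 split 14 and 14 into early and late (an assumed split). The 95% half-width for the difference in mean change is 2.056 × √(2(1−r)) × √(2/14), which is 0.69 SD at r = 0.6 and 0.49 SD at r = 0.8. That is wider than any drift considered here, and neither half has a comparator.

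**The case against.** The strongest reply is that this is a self-described pilot of at most 35 patients. Section 8.3 speaks of obtaining estimates, 30% is called a goal or hypothesis with no formal success rule, and the Protocol disclaims generalizable knowledge. That limits the seriousness of the point and makes a comparator disproportionate. It does not remove the mismatch, because Section 3.0 still says effectiveness and Section 8.2 says the result is to inform practice.

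Three stronger readings are tempting, and the documents do not support them.
- *Natural recovery will be credited to the program.* No section gives a recovery course, rate or direction, and patients on maintenance therapy could worsen. The supportable statement is that change in either direction is inseparable from a program effect.
- *Recovery alone meets the 30% goal.* Step 4 shows that most of the responder share exists with no recovery at all, and at r = 0.9 a drift of 0.2 SD falls short of 30%.
- *Section 8.3 is deficient for not using the treatment dates in Section 6.3.* Covariates and subgroups are commonly left to the SAP, which is not at hand. An early-late contrast would not settle the question either. Gains in late patients also lack a comparator, and gains confined to early patients could mean that the program works better early.

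Regression to the mean also needs a caveat. Section 4.1 sets no FSFI cut-off, so it would arise only if patients tend to join at a low point.

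**Conclusion.** The point holds as a mismatch between the objective in Section 3.0 and the design in Sections 4.3.1, 5.1-5.3 and 8.3. That FSFI change cannot be attributed to the program follows from the design and rests on no numerical assumption. The entry window itself is not an error; it shows why a stable course cannot be presumed.

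The size is illustrative and depends on assumed drift, correlation, normality and alpha. At correlations of 0.6-0.8, an inert program meets the 30% goal with probability 0.13-0.42 without drift and 0.55-0.76 with a drift of 0.2 SD. The goal therefore does not discriminate between a working and an inert program. The sponsor should correct this, but wording suffices and the design need not be rebuilt.

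**What to change.** 1. In Section 3.0, restate the patient FSFI objective as estimating the change in FSFI after the program, in line with Section 1.0.
2. In Sections 3.0 and 8.3, state that, without a comparator, neither the paired t-test nor the 30% goal will be reported as showing the program's effectiveness.
3. Time since treatment may be described from the dates in Section 6.3 (such as "Date of chemotherapy"), but should not be used to support or refute a program effect.
4. Reconcile Section 5.3, which says the two questionnaires will not be linked to each other, with the paired analysis in Section 8.3. Any patient-level change score depends on that link.

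The cost is protocol wording and a more modest claim. No added patients, visits or measurements are needed.

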4.2 Exclusion Criteria

Patient Cohort

- Any records flagged "break the glass" or "research opt-out."
- Patients with severe psychiatric disorders that would impair consent or participation
- Patients with neurological disorders affecting sexual function
- Patients with a history of sexual violence or sexual assault

Nurse Cohort

• Certified Nursing Assistants

4.3 Subject Identification, Recruitment, and Consent

Subjects will be initially identified in the following ways:

Patient Cohort

- The study patient population will be identified from an outpatient cancer center.
- Subjects will be identified through chart audits of patients scheduled to come into clinic who meet the inclusion criteria.

Registered Nurse subjects will be recruited via email, and weekly staff huddles. Emails
will be sent via general email to gynecology oncology nurses and not directly to
individual subjects.

4.3.1 Consent Description

Patient Cohort

APP/Co-PI, [name], will identify patients via medical records. Potential participants will be contacted directly by APP/Co-PI through an IRB-approved email message based on the HRP-661 Direct to Patient Recruitment Letter. The patient will be given the opportunity to decline to be contacted, as indicated in the email. The APP/Co-PI will give the patient a reasonable amount of time to agree to or decline to be contacted after the email is sent. If the patient has already been approached by a treating physician about participation in this study, or if the patient has been sent the recruitment letter and has not declined to be contacted, the APP/Co-PI will reach out to the by phone. In the first conversation with the potential participant, the APP/Co-PI will explain the study carefully by going through the consent form via telephone script. The patient will be given the option to decline or defer participation, or, if interested, to sign the ICF by electronic signature via Docusign. The APP/Co-PI will send the potential participant the DocuSign link to the electronic consent form. Those who prefer to complete the consent form in person will have the option to do so electronically on a tablet or on paper. Patients will be highly encouraged to follow up with the study team before signing should they have any additional questions. If the patient indicates they plan to sign the consent form, the APP/Co-PI will follow up with another phone call if necessary to answer any remaining questions. All patients who participate will receive a surveillance visit with an additional focus on sexual health component with the Advanced Practice Provider ([name]). However, only patients who complete the pre-and post-FSFI survey and complete the APP visit will be involved in the study. The FSFI survey will be submitted to the patient and completed via REDcap.

Nurse Cohort

Information sheet will be given to nurses using REDcap. Nurses will be recruited to participate in the electronic pre and or post survey and informed they may self-select to participate in the project by clicking the survey link and QR code provided to them. A waiver of documentation of informed consent is being requested. By clicking the link, this implies their consent to participate. Nurses will be informed that they may withdraw from participating in the project at any time by exiting the survey. All nurses in the Gynecology Oncology Outpatient Cancer Clinic will receive Sexual Dysfunction training. However, only nurses who agree/consent to the pre-and post-education surveys (KAP & EBPSE) will be involved in the survey.

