5.3 Description of Study Procedures

Patient Cohort

The study involves the participation of patients at multiple time points. The study procedures will assess the patients sexual function using the FSFI prior to the APP sexual health visit and post APP sexual health visit and telephone follow up call. Patients will be recruited through clinical chart identification.

This study involves the participation of registered nurses at multiple time points. The study procedures will assess the nurses' knowledge and confidence using the KAP and EPSE survey before sexual health program and again post education at the end of the study. The survey results will remain anonymous for both the pre and post-test. Nurse subjects will be recruited via email, and staff weekly huddles to complete both surveys.

Medical Record/Clinical Record Review:

Patient Cohort

This study involves review of medical records of patients included in this study. The questionnaire will be administered once at baseline (prior to the APP visit) and at the end of the study (after the telephone follow up call performed 8-10 weeks post APP visit). The study will collect sensitive information. This information is routinely collected per standard of care as as part of clinical care on a regular basis. A study code will be included on the questionnaire. The questionnaire will not be linked to each other and will be administered at two different time points.

- Female Sexual Function Index (FSFI)
 - o The FSFI is a validated tool that addresses five domains: desire, subjective arousal, lubrication, orgasm, satisfaction, and pain/discomfort. It encompasses nineteen self-measurement items that provides a score on overall levels of sexual function (Meston et al., 2020).
- Chart review to count the number of referrals and treatments for sexual dysfunction before and after the nurse led sexual health clinical program intervention

Nurse Cohort- N/A

Education:

Nurse Cohort

- The educational content will come from the After Cancer Solutions for Sexual Health Program, a non-profit developed with input from a cancer survivor and specialists to provide evidence-based education for providers and patients (After Cancer, 2025). The program, including the "About Us" pilot and "30 Second Message Workshop," is active across Iowa and aims to normalize sexual health discussions, build provider confidence, and guide appropriate referrals (After Cancer, 2025).
 - o 30 second message workshop

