8.0 Sample Size and Statistical Considerations

8.1 Sample Size

o This is a single-site study at Cedars-Sinai.

Patient Cohort

- o The sample size of the study will vary between patient subjects.
- The patient data will depend on the number of Gynecological Oncology patients in the outpatient cancer center who have completed treatment in the past 12 months. The goal is to recruit 35 patient participants with 80% completing the pre survey, APP visit, and post survey. Goal of 30% participating patients to report improvement in sexual dysfunction via the FSFI.

Nurse Cohort

- The sample size of the study will vary between nurse subjects.
- The goal for nurse participants is to have 100% gynecological oncology outpatient registered nurses' participation in the pre surveys, sexual health education program, and post surveys.

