8.2 Statistical Sample Size Justification

A statistical sample size is not required because this study involves:

- A pilot study with at most five nurse participants'
- A pilot study with at most 35 patient subjects

 \square Waiver of a sample size justification from the IRB requested due to the following:

- This is an evidence-based practice (EBP) project to inform practice change, not generate generalizable knowledge.
- The sample size is based on the available population within a limited timeframe.

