- In the next survey, EBPSE, we will assess nurses' responses in aggregate form. The EBPSE survey is comprised of 17 items designed to help nurse process information and develop essential EBP skills. Each item is rated on how confident one can perform the activity with percentage numbers 0-100 likert scale (Tucker et al., 2009).
- We hypothesize that 50% of nurses have an increase in EBPSE scores indicated by a ½ standard deviation.
- The project will utilize both QI Macros and Intellectus Statistics to measure the changes in nurses' knowledge and self-efficacy. The analysis will incorporate statistical methods such as run charts, control charts, and t-tests to evaluate changes in participants' knowledge and self-efficacy. More specifically regarding t-tests, the EBPSE will use a paired sample t-test, and the KAP survey will use t-tests to compare pre and post survey responses.

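### The nurse invitation admits one-survey respondents, so the KAP pre and post means could come from different nurses

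*Protocol*

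**What the plan says.** Four parts of the protocol bear on this.

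- **Who is invited (4.3.1, Nurse Cohort).** The invitation reads "Nurses will be recruited to participate in the electronic pre and or post survey". The paragraph ends by saying that "only nurses who agree/consent to the pre-and post-education surveys (KAP & EBPSE) will be involved in the survey". Clicking the link counts as consent, and nurses are told that "they may withdraw from participating in the project at any time by exiting the survey".
- **What is aimed for (8.1, 8.2).** The goal is that all of the clinic's registered nurses take part, with "participation in the pre surveys, sexual health education program, and post surveys". The size is given as "A pilot study with at most five nurse participants".
- **How responses are held (5.3, 6.4).** For the nurses, "The survey results will remain anonymous for both the pre and post-test". The unique ID number in 6.4 is assigned to patients; no equivalent is described for nurses.
- **How they are compared (8.3).** The EBPSE gets a paired-sample t-test, whereas "the KAP survey will use t-tests to compare pre and post survey responses". Responses to both instruments are assessed in aggregate, with run and control charts as well. For each instrument the hypothesis is that half of the nurses improve by half a standard deviation.

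**The concern.** The invitation lets in a nurse who answers one round; the closing sentence of the same paragraph lets in only those who agree to both. The one-survey case is realistic. Every nurse in the clinic is trained whether or not she is surveyed, recruitment is by general email and huddles, and entry is by clicking a link. A trained nurse could therefore first respond at the post survey, and another could answer the pre survey and then leave.

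In a paired analysis such a nurse drops out. In an aggregate or unpaired comparison, which the KAP wording permits, she stays in one mean and is missing from the other. The difference between the means then mixes learning with a change in who answered. The KAP and EBPSE results could also describe different nurses. Because the surveys carry no described code, the analyst could not tell which nurses answered both rounds, even if the intention were to use only those.

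At stake is the secondary objective on nurse knowledge and confidence, not the patient FSFI result.

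**Working it through.** The protocol gives no nurse power calculation, significance level or standard deviation, so there is no figure of its own to reproduce. The check is a comparison of the text followed by arithmetic on the possible shift.

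**1. One nurse read against the text.** Take a nurse who answers only the post survey and never agreed to the pre survey.
- Invitation sentence in 4.3.1: admitted.
- Closing sentence of that paragraph: not involved.
- EBPSE paired test (8.3): cannot contribute.
- KAP t-tests (8.3): may contribute to the post mean, because pairing is not stated.
- Count of nurses improving by half an SD (8.3): cannot contribute, because she has no change score.

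**2. Exact shift with one pre-only and one post-only nurse.** Nurses A, B, C, D answer before; B, C, D, E answer after; nobody's score changes.

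Post mean - pre mean = (B + C + D + E)/4 - (A + B + C + D)/4 = (E - A)/4

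Section 8.3 gives three KAP subscales of 24 to 96 each, so the total runs from 3 × 24 = 72 to 3 × 96 = 288.
- E - A = 20 points: shift = 20/4 = 5 points.
- E - A = 40 points: shift = 40/4 = 10 points. If the between-nurse SD were 20 (assumed), that is 10/20 = 0.5 SD, and A and E would be 40/20 = 2 SD apart.

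**3. Range over who is missing.** Assumptions: five nurses, normal scores with SD 1, no learning, 1,000,000 simulated draws.

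| Membership unrelated to score | Mean shift | SD of false shift | Chance of a false rise of at least 0.5 SD |
|---|---|---|---|
| One nurse misses post | 0 | 0.22 | 1.3% |
| Two nurses miss post | 0 | 0.36 | 8.5% |
| One pre-only, one post-only | 0 | 0.35 | 7.8% |
| Two pre-only, two post-only | 0 | 0.67 | 22.6% |

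The third row agrees with step 2: the SD of (E - A)/4 is √2/4 = 0.35.

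| Membership related to score | Mean shift |
|---|---|
| Lowest scorer misses post | +0.29 SD |
| Two lowest miss post | +0.55 SD |
| Lowest is pre-only, highest is post-only | +0.58 SD |

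**4. Same nurses on both sides.** If only nurses with linked pre and post responses are compared, the shift with no learning is exactly 0 in every row. The number of pairs falls to four with one single-survey nurse and to three with two.

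**The case against.** The best defence is that the intent is clear. The closing sentence of 4.3.1 narrows the loose invitation, the summary describes two time points, and 8.1 aims for everyone at both. The KAP test is never called unpaired, and the handling of incomplete pairs is commonly left to an SAP, which is not at hand. The cohort is at most five nurses in a secondary objective of a pilot. Even the 10-point false shift would be far from significance in an unpaired test of four against four with SD 20: t = 10/(20 × √(1/4 + 1/4)) = 0.71 on 6 degrees of freedom.

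Much of this stands, and it rules out several stronger readings that a reader might infer:
- **That a nurse who leaves after the pre survey is barred.** The closing sentence concerns agreeing to both rounds, not completing them. Someone who agrees and later exits is not excluded by it.
- **That 5.3 separately demands both rounds.** It says "Nurse subjects will be recruited via email, and staff weekly huddles to complete both surveys", but this may mean the KAP and the EPSE; section 5.2 uses two surveys in that sense. The point does not rely on it.
- **That the false shift meets the protocol's half-SD hypothesis.** That criterion counts individual nurses. A one-survey nurse has no change score and cannot be a false improver. Half an SD serves above only as a yardstick for the group mean.
- **That rewording the invitation cures the problem.** Nurses can still exit. New wording can discourage post-only entry but cannot prevent dropout.

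What the defence does not remove is that the invitation and the involvement rule differ within one paragraph, that the protocol itself pairs one instrument and not the other, and that anonymous, uncoded surveys give no described way to form pairs. That last gap affects the EBPSE paired test too.

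**Conclusion.** The point holds in limited form. As written, the KAP comparison can rest on partly different nurses before and after, and nothing described in the protocol would let the analyst detect or correct this. With one pre-only and one post-only nurse the false change is (E - A)/4, which is exact given four respondents per round and no real change. Expressing it as 5 or 10 points assumes differences of 20 or 40 points between those two nurses, and the SD-based figures assume normal scores.

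These are possible sizes. A reader might take them as the expected bias, but the documents do not support that: if membership is unrelated to score the average shift is zero, and if the 100% goal is met there is none. The change is worth making because it is cheap and five nurses leave no room to absorb a change of membership.

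**What to change.** 1. In 4.3.1 and the nurse information sheet, reword the invitation so that it asks nurses to take both the pre and the post survey, in line with the paragraph's closing sentence.
2. Have each nurse enter the same self-generated, non-identifying code on both surveys, and describe this in 5.3 and 6.4. Without it, the nurses who submitted both rounds cannot be found.
3. In 8.3, specify a paired comparison for the KAP as well as the EBPSE, and base the count of nurses improving by half an SD on the same matched nurses.
4. Report pre-only and post-only responses descriptively, against the 100% participation goal.

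The cost is a few sentences and one extra survey field. A code slightly weakens anonymity in a group of five for whom 6.3 already collects age, gender, position and time in position, so the information sheet should say so. Fewer than five pairs may be analysed, but unmatched responses carry no within-nurse information on change.
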